6.3 Visit 3: Operative Visit

Patients will come to one of the University of Pennsylvania Health System hospitals to undergo removal of their tumor as clinically indicated. Surgical approach and exposure are performed according to standard of care. The entire procedure is photo-documented and recorded as per standard of care. There are five phases of NIR imaging; however, one or more of the phases may be omitted. Patients receiving intra-op ICG by anesthesia will report day of surgery and not have an infusion suite visit.

CONFIDENTIAL

This material is the property of the University of Pennsylvania.

Dura View: upon opening the skull at the level of the dura but prior to opening the dura, a brief view of the dura is obtained with the NIR imaging system – Dura View.

Cortex View: upon opening the dura but prior to violating the cortex of the brain, another brief view of the cortex is with the NIR imaging system – Cortex View.

Tumor View: Prior to initial resection but upon identification of the tumor, the NIR imaging system (i.e. VS₃ Iridium, Stryker 1588 AIM) is used to visualize the tumor in its native and untouched form. The lights in the OR are turned off and the infrared imaging system is turned on. The video screen displays the images of the tumor area, and the surgeon measures the spectral reading from the tumor. The imaging system captures the infrared signal that is emitted from the indocyanine green that has been taken up by the tumors. Initial tumor fluorescence will be recorded and visualized. After initial visualization, surgical resection will proceed as per standard of care. A NIR microscope (i.e. Leica FL800, Zeiss INFRARED™ 800) will be used to assist with the surgical resection.

Margin View: After completion of the surgery based on standard techniques, the NIR imaging system (i.e. VS₃ Iridium, Stryker 1588 AIM) will be used to determine if there is any residual fluorescence in the resection bed. In Part 1 of this study, the surgeon will proceed to biopsy suspected areas of residual or abnormal tissue or abnormal fluorescence without extending surgery beyond what is seen on the standard of care MRI. In Part 2 of this study, the surgeon will proceed to resect suspected areas of residual or abnormal tissue or abnormal fluorescence. These biopsy and/or resected sites will be correlated with the final pathology, which will be considered the gold standard. Fluorescence of the biopsy and/or resected specimen with the NIR imaging system will be studied both *in vivo* and *ex vivo*. In addition, surgeon's judgment as to whether the biopsy and/or additional resection specimen represents tumor will be recorded in a binary outcome questionnaire (yes/no).

Final View: Last, prior to closing a final view of the cavity will be obtained with the NIR imaging system – Final View.

Ex Vivo View: Specimens will be placed in a specimen cup. These specimens will be imaged on a back table with the NIR imaging system.

Once the tumor is resected, a small section of the path specimen will be divided and appropriately labelled: 1) histopathology, 2) research lab specimen. Each tissue sample will be placed in its own unique specimen cup. The tissue will be sent to pathology for standard processing, following OSHA and Institutional policy and procedures for tissue handling and transport.

Of note, it is not always possible to be sure of diagnosis prior to surgical sampling and pathologic analysis. Nevertheless, all subjects and specimens will contribute to the final analysis. For example, if the subject is thought to harbor a malignant

CONFIDENTIAL

This material is the property of the University of Pennsylvania.

glioma, but at the time of surgery, an intraoperative diagnosis of lymphoma is made, this subject's pathology and indocyanine green fluorescence status will still contribute to the final analysis plan.

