Oncologic surgery in the brain is always balanced by the potential neurologic/functional risks of additional resection, and for this reason neurosurgeons are always weighing the risks and benefits of additional tumor resection. The addition of the fluorescent dye does not change the calculus for the treating physician/neurosurgeon. The surgeon will continue to weigh the risks and minimize these risks. If he/she thinks that removing the extra tissue is too risky, they will not remove the extra tissue. If removal of additional tissue has minimal risk, the surgeon may choose to remove the additional tissue for diagnostic test considerations.

CONFIDENTIAL

This material is the property of the University of Pennsylvania.

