3.1 General Design

This study is a single center, open-label, two-part study to assess image guided surgery of intramolecular imaging in nervous system tumors. Subjects with a diagnosis of a resectable nervous system tumor who are at risk of recurrence are included. The primary goal is to observe what tissues fluoresce in the OR, and then to identify if that tissue is cancerous/tumor or normal when the histopathology is performed.

This study is split into two parts. The purpose of Part 1 is to confirm dose, assess timing of the operation and assess the feasibility of using indocyanine green as a fluorescent for neurosurgical tumor resection without extending surgery beyond what is seen on the standard of care MRI. The purpose of Part 2 is expansion of the margin view phase of the operation, where residual fluorescence can be resected at the discretion of the surgeon; in addition, further evaluation of optimal dosing and timing.

CONFIDENTIAL

Candidates are those with a presumed tumor in the nervous system that requires surgery. There is no randomization or control group.

Subjects undergo indocyanine green injection within 72 hours prior to surgery. Permitting infusion time within 72 hours of operation is believed to be adequate for tissue glow/surgical visualization. Alternately, patients may receive 25 mg of indocyanine green during induction. Dose and time of administration will be determined by the neurosurgeon during surgical planning. This 25 mg dose of indocyanine green is similar to dosing for other intraoperative vascular visualization.

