3.2 Primary Study Endpoints

The primary end-point of the study is to determine the test characteristics (i.e., sensitivity, specificity, positive predictive value, negative predictive value) of second window indocyanine green in detection of tumors using intraoperative NIR imaging as compared to the standard of care histopathology report.

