7.1 Primary Endpoint

The primary endpoint is the sensitivity, specificity, positive predictive value, negative predictive value of indocyanine green fluorescence as compared to the gold standard – H&E histopathology.

We compute estimates of the sensitivity (fraction of path-positive margins that are called correctly) and specificity (fraction of path-negative margins that are called correctly), and calculate Bayesian 90% probability intervals around them. We estimate the sensitivity of our method by evaluating the fraction of marginal biopsy and/or resected specimens that we call correctly, and similarly estimate the specificity by the fraction of path-negative biopsy and/or resected specimens that we call correctly.

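### Fluorescence helps decide which margin tissue reaches pathology, so section 7.1 measures accuracy among sampled margin specimens, not detection of tumour as section 3.2 presents it

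*Combined protocol and SAP*

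**What the plan says.** Section 3.2 sets the primary endpoint as the "test characteristics (i.e., sensitivity, specificity, positive predictive value, negative predictive value) of second window indocyanine green in detection of tumors", judged against histopathology.

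Section 6.3 (Margin View) says how margin tissue comes to be examined. For Part 1: "In Part 1 of this study, the surgeon will proceed to biopsy suspected areas of residual or abnormal tissue or abnormal fluorescence", within what the standard MRI shows. For Part 2: "In Part 2 of this study, the surgeon will proceed to resect suspected areas of residual or abnormal tissue or abnormal fluorescence". The sites so taken are compared with pathology.

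Section 7.1 estimates sensitivity from the "fraction of marginal biopsy and/or resected specimens that we call correctly" (its preceding sentence limits this to path-positive margins) and specificity from the "fraction of path-negative biopsy and/or resected specimens that we call correctly". It gives Bayesian 90% intervals, with no adjustment or caveat for tissue that was not sampled.

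Not every fluorescent area need be taken. Section 3.1 says that in Part 2 "residual fluorescence can be resected at the discretion of the surgeon", and section 1.7.1 says: "If he/she thinks that removing the extra tissue is too risky, they will not remove the extra tissue".

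Bulk tumour also goes to pathology. Section 6.3 says that "all subjects and specimens will contribute to the final analysis", without saying whether bulk and margin specimens are analysed apart.

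**The concern.** Fluorescence is the index test and pathology is the reference standard. When a positive index test is itself a reason to obtain the reference standard, accuracy computed on the verified specimens generally differs from accuracy over all the tissue at risk. This is partial verification. Here, margin that is neither fluorescent nor suspected has no systematic route to pathology, so false negatives and true negatives are counted only where the surgeon had some other reason to sample.

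Section 7.1 is open about its denominator. The trouble is that section 3.2 attaches a wider meaning to the same numbers. A reader would take the primary sensitivity and specificity as a statement of how well near-infrared imaging separates tumour from normal tissue in the resection bed. Section 7.3 says the study is to inform a future randomised study, so the figures may be carried forward with that meaning.

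**Working it through.** **Inputs.** The documents give the sampling rule (6.3), the denominators (7.1) and the latitude to leave fluorescent tissue (1.7.1, 3.1). They give no sampling rates, no expected accuracy and no sample size calculation (7.3), so there is no plan figure to reproduce. Every number below is assumed.

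**Formulas.** Let P be the share of candidate margin sites that are tumour. Let a1 and a0 be the sampling probabilities of fluorescent tumour and fluorescent normal sites, and q1 and q0 those of dark tumour and dark normal sites. The test call is taken to be the in vivo reading.

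- Apparent Se = Se·a1 / (Se·a1 + (1−Se)·q1). Correct only if a1 = q1; too high if a1 > q1, too low if a1 < q1.
- Apparent Sp = Sp·q0 / (Sp·q0 + (1−Sp)·a0). Correct only if a0 = q0; too low if a0 > q0, too high if a0 < q0.
- Apparent PPV is correct only if a1 = a0.
- Apparent NPV is correct only if q1 = q0.

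**Scenarios.** Take P = 50% and true Se = Sp = 70%, so true PPV = NPV = 70%. Per 1,000 sites there are 350 fluorescent tumour, 150 dark tumour, 150 fluorescent normal and 350 dark normal.

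| Scenario | a1, a0, q1, q0 | TP, FN, FP, TN | Se | Sp | PPV | NPV |
|---|---|---|---|---|---|---|
| A: all fluorescent sites taken; surgeon suspects 30% of tumour and 10% of normal sites | 1, 1, 0.3, 0.1 | 350, 45, 150, 35 | 89% | 19% | 70% | 44% |
| B: as A, but half of unsuspected fluorescent sites left | 0.65, 0.55, 0.3, 0.1 | 227.5, 45, 82.5, 35 | 83% | 30% | 73% | 44% |
| C: half of fluorescent sites taken; dark tumour often suspected | 0.5, 0.5, 0.6, 0.1 | 175, 90, 75, 35 | 66% | 32% | 70% | 28% |

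In B, a1 = 0.3 + 0.7·0.5 = 0.65 and a0 = 0.1 + 0.9·0.5 = 0.55. In C, fluorescent sites are taken twice as often as dark ones overall (250/500 = 50% against 125/500 = 25%), yet apparent Se is 175/265 = 66%, below the true 70%. The comparison of sampling rates has to be made within tumour and within normal tissue separately.

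**Other true values.** With Se = 70% and Sp = 80%, sampling at a1 = a0 = 1, q1 = 0.5, q0 = 0.2 gives Se 82% and Sp 44%. With a1 = a0 = 0.3 and the same q1 and q0, Se is 58% and Sp 73%.

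**NPV.** With P, Se and Sp as in the table, NPV = 350 / (350 + 150r), where r = q1/q0. This gives 70% at r = 1, 54% at r = 2, 44% at r = 3 and 32% at r = 5. Only the ratio matters: halving 30% and 10% to 15% and 5% leaves NPV at 44%.

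**What a by-reason table can show.** In A, 380 of 580 specimens (66%) are taken for fluorescence alone. They can only be TP (350·0.7 = 245) or FP (150·0.9 = 135). The 200 suspected specimens (TP 105, FN 45, FP 15, TN 35) give Se 105/150 = 70% and Sp 35/50 = 70%. That recovery needs suspicion to be independent of fluorescence given pathology. If suspicion is 40% and 20% in fluorescent and dark tumour, and 20% and 10% in fluorescent and dark normal tissue, the suspected stratum gives Se 140/170 = 82% and Sp 35/65 = 54%. The table is informative but is not a correction.

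**What bounds can show.** In B, 310 of 500 fluorescent sites are sampled and PPV is 227.5/310 = 73%. With the 190 unsampled sites counted all as normal or all as tumour, the bounds are 227.5/500 = 46% (45.5%) and 417.5/500 = 84% (83.5%).

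**The case against.** **Section 7.1 names its denominator, and section 7.4 calls the analyses primarily descriptive.** Both are true, and no accuracy threshold drives a decision. This limits the remedy to labelling, a table and bounds. It does not reconcile section 3.2 with section 7.1.

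**A reader might infer that sensitivity must be inflated and specificity deflated.** The documents do not support that. It follows only if fluorescent sites are sampled more often than dark ones within each pathology class. Sections 1.7.1 and 3.1 allow fluorescent tissue to be left, and scenario C shows sensitivity moving the other way.

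**A reader might infer that dark, unsuspected margin can never reach pathology.** Section 1.7.1 also lets the surgeon remove additional low-risk tissue for the sake of the diagnostic test. That route is optional, has no rule or number, and in context probably concerns fluorescent tissue. It qualifies the point without answering it.

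**Some of the needed data are already planned.** Section 6.3 records the surgeon's yes/no judgment of whether each margin specimen is tumour, studies fluorescence in vivo and ex vivo, and includes a Final View before closing. This stands and makes the fix cheaper. The judgment is not a reason for sampling, however, and the text does not say whether it comes before near-infrared viewing. Views may also be omitted. The case report forms are attachments not available here, so one can say only that the visible text asks for no count of unsampled fluorescent areas.

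**A reader might infer that dose and timing would be chosen on biased accuracy.** Sections 1.6, 3.3 and 7.2 rest that choice mainly on signal to background ratio, with safety. Only the objectives (the Study Summary and section 2) tie it to sensitivity and specificity. Under that wording, two groups with an identical dye but the habits of A and B would differ by 5 points in sensitivity (88.6% − 83.5%) and 11 in specificity (29.8% − 18.9%). The consequence goes no further.

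**The illustrations assume a countable set of candidate sites and an in vivo call.** Neither is defined in the plan. On an ex vivo call, specimens taken for fluorescence could also be FN or TN. This is a reason to state which reading is the test call.

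**Conclusion.** The point holds and should be fixed. As planned, the primary sensitivity, specificity, PPV and NPV describe margin specimens that a surgeon chose to sample, partly because of the test result. They do not estimate detection of residual tumour in the resection bed, which is how section 3.2 would be read. The claim concerns margin tissue only.

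The mismatch rests on the text alone. The size does not: with no sampling rates in the documents, neither magnitude nor direction can be derived, and figures such as 89% and 19% against a true 70% show only that the distortion can be large under plausible-looking assumptions.

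**What to change.** 1. In sections 3.2 and 7.1, define the primary measures as accuracy among sampled margin specimens and state that they do not estimate detection of residual tumour in the resection bed. State whether the in vivo or the ex vivo reading is the test call. Report bulk tumour specimens separately.
2. Tabulate fluorescence against pathology by reason for sampling (suspicion, fluorescence or both). Build on the surgeon's yes/no judgment in section 6.3 and add a reason code that notes whether suspicion preceded near-infrared viewing. Add a sensitivity analysis over assumed sampling rates for fluorescent and dark sites, separately within tumour and within normal tissue.
3. For remaining subjects, unless the case report form already captures it, count fluorescent margin areas seen but not sampled, using the Margin View and Final View and a simple rule (for example, each separate contiguous area counts once). Report PPV with worst-case and best-case bounds.

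For subjects already treated, do items 2 and 3 only where records allow. At the January 2019 status in section 1.5, about 177 subjects remained (500 − 327 + 4) if the cap counts consented subjects. Some of these would not be evaluable, as 26 of the 327 were not, and fewer remain if more have been treated since.

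The cost is some wording, one code per margin specimen, one count per subject, one table and one sensitivity analysis. The price is a less favourable headline and wide bounds. On the scenario A cells, with all fluorescent sites taken, assuming 10% to 50% sampling of dark tumour gives corrected Se from 350/(350 + 450) = 44% to 350/(350 + 90) = 80%. The bias is labelled and bounded, not removed. No change to what tissue is removed is proposed.

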6.4 Annual Assessments and Subject Follow-Up

For a period of up to 5 years after enrollment, the PI and research team will review the subjects' medical records annually to obtain information about their medical condition. Re-occurrence will be tracked with the subject's oncologist. We utilize the standard protocol used by the oncologist for tracking re-occurrence, which includes, but is not limited to MRI, CT, or PET scans.

6.5 Rescue Therapy

There is a possibility of anaphylaxis in patients with iodide allergies and these patients are not considered candidates in this study. Anaphylaxis is a reversible condition when treated quickly, and our subject population is monitored at the time of injection (see [Section 8.2](#)).

7 Statistical Plan

7.1 Primary Endpoint

The primary endpoint is the sensitivity, specificity, positive predictive value, negative predictive value of indocyanine green fluorescence as compared to the gold standard – H&E histopathology.

We compute estimates of the sensitivity (fraction of path-positive margins that are called correctly) and specificity (fraction of path-negative margins that are called correctly), and calculate Bayesian 90% probability intervals around them. We estimate the sensitivity of our method by evaluating the fraction of marginal biopsy and/or resected specimens that we call correctly, and similarly estimate the specificity by the fraction of path-negative biopsy and/or resected specimens that we call correctly.

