7.4 Statistical Methods

All data are summarized, with means and standard deviations for continuous variables and proportions for categorical variables. Graphical techniques will be used for data exploration. Analyses will be primarily descriptive. The remainder of the statistical approaches is described above.

8 Safety and Adverse Events

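### Section 7.1 gives two conflicting denominators for sensitivity and no rule for how several specimens from one patient enter the Bayesian 90% interval

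*Combined protocol and SAP*

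**What the plan says.** Section 7.1 (Primary Endpoint) describes each measure twice. The defining sentence gives "sensitivity (fraction of path-positive margins that are called correctly" and "specificity (fraction of path-negative margins that are called correctly". The estimating sentence that follows reads "We estimate the sensitivity of our method by evaluating the fraction of marginal biopsy and/or resected specimens that we call correctly" and then "similarly estimate the specificity by the fraction of path-negative biopsy and/or resected specimens that we call correctly".

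On uncertainty, the plan says only that it will "calculate Bayesian 90% probability intervals around them".

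On what enters the analysis, the Margin View text in Section 6.3 speaks of suspected areas and sampled sites in the plural and states: "These biopsy and/or resected sites will be correlated with the final pathology, which will be considered the gold standard". The same section adds: "Nevertheless, all subjects and specimens will contribute to the final analysis". Section 7.4 supplies no further method. It calls the analyses primarily descriptive and closes with "The remainder of the statistical approaches is described above".

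**The concern.** There are two gaps in the working definition of the primary endpoint.

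**Denominator.** Sensitivity should not depend on how many of the sampled specimens contain tumor. Overall accuracy does. If the estimating sentence were followed as written, the figure labelled sensitivity would move with the path-positive share even if fluorescence performed identically. That share may well vary here: Part 1 surgeons biopsy suspected areas, Part 2 surgeons resect them, and tumor types are mixed. The Study Summary also makes sensitivity and specificity the basis for optimizing dose and timing (Part IIb), so a figure that shifts with case mix could mislead those comparisons.

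**Interval.** The estimates are proportions of specimens, and one patient can supply several. Results within a patient are likely to be correlated, since dose, timing, tumor and camera are shared. The plan neither states that specimens are pooled as independent nor excludes it. A pooled interval would be too narrow whenever patients contribute more than one specimen of the same pathology status with correlated results.

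Section 7.3 gives no sample size calculation and says the study is meant to inform a later randomized trial. The estimates and their intervals are therefore the main product.

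**Working it through.** **There is no plan figure to reproduce.** The documents give no expected sensitivity or specificity, precision target, specimens per patient or within-patient correlation. All inputs below are assumptions, shown as ranges.

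**1. The text side by side.**

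| Measure | Defining sentence | Estimating sentence |
|---|---|---|
| Sensitivity | path-positive margins | marginal biopsy or resected specimens, no pathology restriction |
| Specificity | path-negative margins | path-negative biopsy or resected specimens |

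The restriction is missing from one cell of four, and the unit moves from margins to specimens.

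**2. Size of the denominator effect.** Let Se be sensitivity, Sp specificity and π the share of specimens that are path-positive. The literal estimating sentence gives

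(TP + TN) / all specimens = π·Se + (1 − π)·Sp,

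which differs from Se by (1 − π)(Sp − Se). For example, 0.7 × 0.90 + 0.3 × 0.50 = 0.78.

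| Assumed Se / Sp | π = 0.9 | 0.7 | 0.5 | 0.3 |
|---|---|---|---|---|
| 0.90 / 0.50 | 0.86 | 0.78 | 0.70 | 0.62 |
| 0.90 / 0.80 | 0.89 | 0.87 | 0.85 | 0.83 |
| 0.70 / 0.90 | 0.72 | 0.76 | 0.80 | 0.84 |
| 0.80 / 0.80 | 0.80 | 0.80 | 0.80 | 0.80 |

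The error can go either way. It vanishes when Se = Sp or when every specimen is path-positive.

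In counts: take 140 path-positive specimens with 126 called correctly, and 60 path-negative with 30 called correctly. With a Beta(1,1) prior,
- path-positive denominator: 126/140 = 0.900, 90% interval 0.849 to 0.933;
- literal second sentence: (126 + 30)/200 = 0.780, 90% interval 0.728 to 0.824.

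The two intervals do not overlap.

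**3. Size of the clustering effect, only if specimens are pooled as independent.** Let m be the number of specimens of the relevant pathology status per patient and ρ their within-patient correlation. The design effect is D = 1 + (m − 1)ρ. The correct interval is wider by about √D, and a pooled nominal 90% interval covers about 2Φ(1.645/√D) − 1.

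This was checked by simulation: 20,000 runs per setting, 100 and 300 patients, beta-binomial clusters with true proportion 0.85, and a pooled Beta(1,1) interval.

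| m, ρ | D | √D | Coverage by formula | Simulated, m fixed | Simulated, m = 1 + Poisson with the same mean |
|---|---|---|---|---|---|
| 2, 0.1 | 1.1 | 1.05 | 0.88 | 0.88 to 0.89 | about 0.88 |
| 3, 0.3 | 1.6 | 1.26 | 0.81 | 0.80 to 0.82 | about 0.78 |
| 5, 0.5 | 3.0 | 1.73 | 0.66 | 0.65 to 0.66 | about 0.63 |

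With one specimen per patient, or ρ = 0, pooled coverage is 0.89 to 0.91. With a mean of 1.2 specimens and ρ of 0.1 to 0.3 it is 0.88 to 0.90. So there is little or no effect in those cases.

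A cluster-robust ratio interval covered about 0.88 to 0.90 for m of 2 or more. At 100 patients with m fixed, its width relative to the pooled interval was 0.0868/0.0826 = 1.05, 0.0853/0.0674 = 1.27 and 0.0906/0.0523 = 1.73, in line with √D.

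**The case against.** The denominator point can be read as a drafting slip. The correct definition stands in the sentence before, overall accuracy is not an endpoint anywhere, and the specificity clause shows what was meant. A careful analyst would probably use path-positive specimens. That is likely true, and it lowers the chance of harm. It does not remove the conflict: the faulty sentence is the one that says how the primary endpoint is estimated, and no text gives the other precedence.

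On clustering, the statement in Section 6.3 that all specimens contribute is made in the context of diagnoses that change at surgery, not as a pooling rule. The harm also needs several conditions at once: multiple specimens, the same pathology status, correlated results and pooling as independent. The documents establish only that the first is possible, and the lowest coverages rest on cluster sizes and correlations that nothing in them supports. This stands as a limit on the size of the effect. It does not answer the silence on prior, model and unit of analysis, where two competent analysts could differ.

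It is also fair that the analyses are primarily descriptive and that no test, threshold or stopping rule uses the interval. Finally, a cluster bootstrap would not be a Bayesian interval, and the interval simulated above is cluster-robust rather than hierarchical. The simulation shows what ignoring clustering costs. It does not validate a particular Bayesian model.

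**Conclusion.** Both parts hold on the text. Section 7.1 contradicts itself on the denominator of sensitivity, most likely through a dropped word, and it leaves the interval unspecified where patients contribute several specimens.

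The size cannot be fixed from the documents. Under the assumptions shown, the denominator error runs from nil to 0.28 (0.90 reported as 0.62). Loss of coverage from pooling runs from nil to about 27 percentage points (0.90 to 0.63), with the large values only at high cluster size and correlation. The harm is to the accuracy and stated precision of reported figures, not to a formal decision. The section should be corrected before the final analysis: the study is open-label, and 296 subjects had been infused by January 2019, so a choice left open could be made with the data in view.

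**What to change.** In Section 7.1:

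- **Denominators.** Insert path-positive in the estimating sentence. Sensitivity is then path-positive specimens called fluorescent over all path-positive specimens; specificity is path-negative specimens called non-fluorescent over all path-negative specimens. If overall accuracy is wanted, report it under its own name.
- **Interval.** Name the specimen as the unit of analysis, and state the prior and a model with a patient-level term. A hierarchical logistic or beta-binomial model keeps the Bayesian interval already promised. A patient-level cluster bootstrap could serve as a check.
- **Reporting.** Give the number of path-positive and path-negative specimens per patient, so that readers can see whether clustering matters.

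The cost is one inserted word, two sentences on the interval and one descriptive tabulation, with no new data and no change to procedures. The interval will be somewhat wider if patients contribute several correlated specimens, and almost unchanged if most contribute one.
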